#### 5.1.1. Screening

Before a subject's participation in the clinical study, the Investigator is responsible for obtaining written informed consent from the subject after adequate explanation of the study design, anticipated benefits, and the potential risks.

The following procedures/assessments will be performed at the Screening Visit (within 4 weeks after signing the informed consent):

- Review of medical and surgical history, including any history of allergies
- Review of childbearing potential (subject or partner of male subject) and contraceptive use ([Section 5.1.2](#))
- Collection of demographic data including sex, age, race, ethnicity
- Limited physical examination of skin, lungs, and heart
- Vital signs including weight, temperature, heart rate, and blood pressure
- ECG
- Medical history of vitiligo will include the following information, which will be recorded in the CRF:
  - Location (ie, face, neck, hands, forearms)
  - Distribution/Characteristics: Presence of confetti, trichrome, or inflammatory vitiligo lesion patterns or other clinical signs of active vitiligo
- Assessment of Fitzpatrick skin type

- BSA Assessments (F-BSA, F/N-BSA, BSA (hands, forearms, elbows), BSA (total body))
- Vitiligo assessments (F-VASI, F/N-VASI, FOREARM-VASI, HAND-VASI, T-VASI, and FsIGA)
- Laboratory tests: hematology, chemistry, urinalysis, TSH, T4, serum pregnancy test (for female subjects of childbearing potential), FSH (if indicated to confirm post-menopausal status)
- Collection of concomitant medications and adverse events

All screened subjects will receive a screening number and will be entered into the Interactive Response Technology (IRT) system at the time of consent.

Subjects may be re-screened one time, the original assigned Subject ID screening number will be used for re-screening.

### **5.1.2. Contraception Requirements**

[figure not shown]
Previous nonclinical research showed that the active ingredient in ARQ-252 can harm fetal development. Subjects engaging sexual intercourse that could lead to pregnancy must adhere to the following pregnancy testing and/or contraception requirements.

#### **Female Subjects:**

Female subjects of childbearing potential (FOCBP) must have a negative serum pregnancy test at Screening and negative urine pregnancy test at Baseline (Visit 2). For FOCBP involved in any sexual intercourse that could lead to pregnancy: the subject must agree to use a highly effective contraceptive method for at least 4 weeks prior to Day 1. Additionally, from Day 1 until at least 4 weeks after the last investigational product administration, these subjects must agree to use at least 1 highly effective contraceptive method in addition to 1 barrier method of contraception.

The acceptable methods of contraception are listed below in the [Figure 1](#).

**Figure 1: Contraception Requirements for Female Subjects**

Subjects using hormonal contraceptives must have been on a stable dose for at least 4 weeks before Day 1.

The above list of contraceptive methods does not apply to subjects who are abstinent for at least 4 weeks before Day 1 and will continue to be abstinent from penile-vaginal intercourse throughout the study. The reliability of sexual abstinence needs to be evaluated in relation to the duration of the clinical trial and the preferred and usual lifestyle of the participant.

Female condom and male condom should not be used together.

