###### **Main Criteria for Inclusion:**

1. Subject is legally competent to sign and give informed consent.
2. Males and females ages 18-21 years with Fitzpatrick Skin Type IV-VI or age 22 years and older with Fitzpatrick Skin Type I-VI.
3. Clinical diagnosis of non-segmental vitiligo involving face.
4. A Facial Vitiligo Area Severity Index [F-VASI] score of  $\geq 0.25$  at baseline.

5. Vitiligo of the face involving at least  $\geq 0.25\%$  body surface area (BSA) involvement (ie, one quarter of one handprint). Subjects may have non-facial vitiligo elsewhere which will not be included in the minimum BSA. The maximum BSA (total body inclusive of the face, whether or not in areas to be treated in this study) permitted is 15%.
6. Subjects with vitiligo on the hands, forearms, or elbows agree to treat these areas in addition to the face, with investigational product and phototherapy.
7. Subject agrees to discontinue all agents used to treat vitiligo from screening through the final safety follow-up visit. Over-the-counter preparations deemed acceptable by the Investigator and camouflage makeups are permitted.
8. Female subject of childbearing potential (FOCBP) must have a negative serum pregnancy test at Screening and negative urine pregnancy test at Baseline (Visit 2). For FOCBP involved in any sexual intercourse that could lead to pregnancy: the subject must agree to use a highly effective contraceptive method for at least 4 weeks prior to Day 1. Additionally, from Day 1 until at least 4 weeks after the last investigational product administration, these subjects must agree to use at least 1 highly effective contraceptive method in addition to 1 barrier method. [Figure 1](#)
9. Female subject of non-childbearing potential must either be post-menopausal with spontaneous amenorrhea for at least 12 months prior to baseline (post-menopausal status will be confirmed with FSH testing) or have undergone surgical sterilization (permanent sterilization methods include hysterectomy, bilateral oophorectomy, or bilateral salpingectomy). [Figure 1](#)
10. Males, if engaging in sexual intercourse with a female who is pregnant or a female of child-bearing potential, must agree to use a condom every time during the study and every time subsequently until 4 weeks beyond the last dose of investigational product.
11. Males must agree not to donate sperm from the first dose of investigational product until 4 weeks after the last dose of investigational product.

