22. Subjects with severe renal insufficiency (as evidenced by estimated glomerular filtration rate <40 mL/min) or with severely impaired liver function (Child-Pugh Class C), ALT or AST  $\geq 2 \times$  ULN, total bilirubin  $> 1.5 \times$  ULN, or total bilirubin  $>$  ULN and  $\leq 1.5 \times$  ULN AND direct bilirubin is  $> 35\%$  of total bilirubin, ALP  $\geq 2x$  ULN.
23. [REDACTED]
24. Pregnant or lactating women or women planning to become pregnant during the study and / or within 28 days following the last dose of investigational product.
25. Subjects who cannot discontinue the use of strong systemic Cytochrome P-450 CYP3A4 inducers e.g., efavirenz, nevirapine, glucocorticoids, barbiturates (including phenobarbital), phenytoin, rifampin and carbamazepine for 2 weeks prior to Baseline and during the study period.
26. Subjects who cannot discontinue the use of strong systemic Cytochrome P-450 CYP3A4 inhibitors e.g., indinavir, nelfinavir, ritonavir, clarithromycin, itraconazole, ketoconazole, fluconazole, nefazodone, saquinavir, suboxone and telithromycin for 2 weeks prior to Baseline and during the study period.
27. Any dermatologic condition that in the Investigator's assessment would preclude the subject from participating in the study.
28. Subjects who, in the opinion of the Investigator, are unable or unlikely to comply with the administration schedule and study evaluations.

29. Subjects who are family members of the clinical study site, clinical study staff, or sponsor, or family members that live in the same house of enrolled subjects.

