## Male Subjects:

Males, if engaging in sexual intercourse with a female who is pregnant or a female of childbearing potential, must agree to use a condom every time during the study and every time subsequently until 4 weeks after the last investigational product administration.

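### The abstinence exemption in Figure 1 footnote 2 ends with the study, nominally 20 to 21 days before the protocol's own 4-week post-dose window closes

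*Protocol*

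**What the plan says.** Protocol Section 5.1.2 gives the reason for its contraception rules: "Previous nonclinical research showed that the active ingredient in ARQ-252 can harm fetal development". For women the rule begins "For FOCBP involved in any sexual intercourse that could lead to pregnancy" and asks for a highly effective method before Day 1. It then continues: "from Day 1 until at least 4 weeks after the last investigational product administration, these subjects must agree to use" one highly effective method plus one barrier method. Inclusion criterion 8 (Section 4.5.1 and the Synopsis) repeats this.

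Footnote 2 to Figure 1 sets an exemption. The list of methods does not apply to a woman who has been abstinent for the 4 weeks before Day 1 and who "will continue to be abstinent from penile-vaginal intercourse throughout the study". The next sentence concerns how far the abstinence can be relied on: "The reliability of sexual abstinence needs to be evaluated in relation to the duration of the clinical trial", and to the participant's usual lifestyle. Neither sentence mentions the weeks after the last dose.

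Elsewhere the protocol names those weeks separately from the study. Men "must agree to use a condom every time during the study and every time subsequently until 4 weeks after the last investigational product administration" (Section 5.1.2, Male Subjects). Exclusion criterion 24 (Section 4.5.2) excludes women who plan a pregnancy "during the study and / or within 28 days following the last dose of investigational product".

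**The concern.** For an exempt woman, abstinence takes the place of two contraceptive methods, so it should last as long as they would. As footnote 2 is worded, both her commitment and the investigator's check on it finish with the study. The period that the protocol itself treats as at risk runs on to 4 weeks after the last dose.

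The Schedule of Visits and Assessments (Section 1.3) shows no visit and no pregnancy test after Week 25. In the remaining weeks, protection rests mainly on what the woman agreed to beforehand. What is at stake is fetal and subject safety. No endpoint, test or sample-size figure depends on it.

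**Working it through.** **Inputs**
- Week 24 is Day 169 and Week 25 is Day 176, each with a window of 7 days either way (Section 1.3).
- A subject has up to 5 weeks of screening, 24 weeks of treatment and 1 week of follow-up, 30 weeks in all (Synopsis, Duration of Treatment). The final visit is at about Week 25 (Section 5.4).
- The post-dose period is 4 weeks, or 28 days (Section 5.1.2; criterion 24 says 28 days).
- The day of the last dose is an assumption. The Schedule marks no in-clinic application at Week 24, and its PK footnote asks for an application 11 to 12 hours before the sample. The last dose is therefore taken as Day 168 (the evening before) or Day 169.

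**1. Reproduce the protocol's calendar.** Visit day = 7 × week + 1. This gives 7 × 24 + 1 = 169 and 7 × 25 + 1 = 176; total time is 5 + 24 + 1 = 30 weeks. All agree with the protocol.

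**2. Close of the post-dose window.** Last dose + 28: 168 + 28 = 196, or 169 + 28 = 197.

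**3. Shortfall of the abstinence condition.** Close of window minus final visit: 196 − 176 = 20 days, or 197 − 176 = 21 days.

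**4. Sensitivity to visit timing.** If the Week 25 visit is held 7 days after the Week 24 visit, the shortfall is 28 − 7 = 21 days when the last dose is on the Week 24 visit day, and 28 − 8 = 20 when it is the day before, wherever the pair falls. If the two windows move independently, the smallest shortfall has Week 24 on Day 162, Week 25 on Day 183 and the last dose on Day 161: 161 + 28 − 183 = 6 days. For a subject who attends within the windows, scheduling alone does not close the gap.

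**5. Does the study include the post-dose weeks?** The condom rule for men and exclusion criterion 24 each list the study and the post-dose period as two things. If the study already covered the 4 weeks, the second limb would be redundant. Footnote 2 has only the first limb.

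**6. The alternative meaning of the study.** Section 7.3.1 says the study completes at the last visit of the last subject. On that reading, the length of a woman's commitment depends on when other subjects finish. The shortfall is still 20 to 21 days for the last subject to finish, and nil for one who finished 21 or more days earlier.

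**7. With the condition tied to the last dose.** Required end of abstinence = last dose + 28 = close of window, so the shortfall is 0.

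**The case against.** The strongest reply is that Section 5.1.2 works by conduct, not by status at enrolment. Its opening paragraph places the requirements on subjects who have intercourse that could lead to pregnancy, and the 4-week period follows from that. Footnote 2 lifts only the list of methods; it does not shorten the period. A woman who resumes intercourse on Day 180 can be read to fall under the rule from then on. Criterion 24 also applies to her. In addition, SAEs are collected to 30 days after the last application or the end of study, whichever is later (Sections 5.1.9 and 5.7.2), and a confirmed pregnancy is followed to its conclusion (Section 5.8).

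Much of this stands. A reader might infer that an exempt woman has no protection or obligation for 20 or 21 days of the 28. The documents do not support that: the count measures how far one condition falls short, not days without any requirement. What the reply does not reach is the abstinence condition itself. The two-method agreement is asked of women having such intercourse, so the visible text asks an abstinent enrollee for no advance commitment covering those weeks. Criterion 24 concerns planned pregnancy only, and SAE collection does not prevent conception.

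The body of Figure 1 and the consent pages are not available here, and either might state a longer period. That lowers confidence. It does not alter the end point written in the footnote.

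**Conclusion.** The point holds as a mismatch between one footnote and the protocol's own risk window. On the nominal schedule, the abstinence condition and the related reliability check end 20 to 21 days before the 4-week window closes. This assumes a last dose on Day 168 or 169, a final visit on Day 176, and that the study means the subject's own participation. The Synopsis supports that last assumption, as do the two places that name the post-dose period separately.

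Three further readings are tempting and go too far:
- **A shortfall of the full 4 weeks.** This needs the Week 24 and Week 25 visits on the same day, contrary to the planned week of follow-up.
- **A figure for early terminations.** Section 5.5 gives no interval between the last dose and the exit visit, so none can be computed.
- **A matching fault in Section 5.8.** Its opening words may only date when the pregnancy-reporting instruction is given, so no defect is shown there.

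Severity is low. The 4-week intent is explicit in several other sections, and the documents do not say how many women would use the exemption. There is no effect on endpoints, alpha or power.

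**What to change.** In Figure 1 footnote 2, extend the abstinence condition beyond the study so that it runs until at least 4 weeks after the last administration of investigational product, the end point already set in Section 5.1.2. In the next sentence, extend the period over which reliability is judged to the same date.

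The cost is two phrases. Exempt women would commit to about three more weeks of abstinence, and some may choose a listed method instead. No subjects, visits or tests are added. SAP Section 3 reports that the trial was stopped and enrolled subjects were terminated early, so the practical value lies mainly in any later protocol that reuses this footnote.

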## Male Subjects:

Males, if engaging in sexual intercourse with a female who is pregnant or a female of childbearing potential, must agree to use a condom every time during the study and every time subsequently until 4 weeks after the last investigational product administration.

### 5.1.3. Physical Examination

Physical examinations will be performed according to the Schedule of Visits and Assessments (Section 1.3). The physical exam will be limited to skin, lungs and heart only.

### 5.1.4. Vital Signs, Height and Weight

Vital signs will be performed according to the Schedule of Visits and Assessments (Section 1.3). Blood pressure, heart rate, and temperature will be collected in seated position after approximately 5 mins. Subjects will be instructed to void prior to weight being taken and to remove any objects of significant weight (i.e., jackets, outerwear, shoes, cell phones, wallet, key chains, etc.).

Height will be measured at Baseline (Day 1) only.

### **5.1.5. Fitzpatrick Skin Type Assessment**

At screening, Fitzpatrick skin phototype will be rated:

- I: Always burns easily; never tans (sensitive)
- II: Always burns easily; tans minimally (sensitive)
- III: Burns moderately; tans gradually (light brown) (normal)
- IV: Burns minimally; always tans well (moderate brown) (normal)
- V: Rarely burns; tans profusely (dark brown) (insensitive)
- VI: Never burns; deeply pigmented (insensitive)

### **5.1.6. 12-lead ECGs**

12-lead ECGs will be performed according to the Schedule of Visits and Assessments (Section 1.3).

ECGs will be obtained on subjects after approximately 5 minutes in the supine position. All ECG tracings and readouts will be reviewed by the Investigator and central reader at the ECG laboratory.

### **5.1.7. Laboratory Tests**

Hematology	Serum Chemistry

• Hemoglobin

• Hematocrit

• Total and differential leukocyte count

• Red blood cell count with indices and morphology

• Platelet count

• Reticulocyte count

	

• Blood Urea Nitrogen

• Bilirubin (total and direct)

• Alkaline phosphatase

• Aspartate aminotransferase

• Alanine aminotransferase

• Albumin

• Sodium

• Potassium

• Chloride

• Glucose

• Creatinine

• Creatine kinase

Urinalysis	Additional Tests

• pH

• Specific gravity

• Protein

• Glucose

• Ketones

• Bilirubin

• Blood

• Nitrite

• Urobilinogen

• Leukocyte esterase

	

• Thyroid Stimulating Hormone T4 (TSH/T4)

• Urine pregnancy test (for females of childbearing potential only)

• Serum pregnancy test (hCG)

• Follicle-stimulating Hormone (FSH)

• Pharmacokinetic (PK) assessments

• Fasting Lipids (cholesterol, triglycerides, HDL, and LDL)

**From table above:**

 If red blood cell count, hemoglobin or hematocrit values are below the lower limit of normal, reticulocyte count will be performed

 If urinalysis is positive for protein, blood, nitrite and/or leukocyte esterase, a microscopic examination (for red blood cells, white blood cells, bacteria, casts, and epithelial cells) will be performed.

 At Baseline, Week 4, 8, 12, 16, 20, and 24 for FOCBP only.

 At screening only for FOCBP.

 If indicated to confirm post-menopausal status

 Fasting required for a minimum of 8 hours prior to blood draw

### **5.1.8. Local Tolerability Assessment**

The Investigator Local Tolerability Assessments will be performed according to the Schedule of Visits and Assessments ([Section 1.3](#)). Application site reactions are graded using the scale detailed in the following section ([Berger 1982](#)).

The Investigator Local Tolerability Assessment will be conducted by the Investigator **prior to investigational product application** in the clinic.

**Investigators will specify if any application site reaction is due, in whole or in part, to the effects of phototherapy treatment.**

#### Dermal Response

0. no evidence of irritation
1. minimal erythema, barely perceptible
2. definite erythema, readily visible; minimal edema or minimal papular response
3. erythema and papules
4. definite edema
5. erythema, edema, and papules
6. vesicular eruption
7. strong reaction spreading beyond application site

#### Other Effects

- A. = slight glazed appearance
- B. = marked glazing
- C. = glazing with peeling and cracking
- D. = glazing with fissures
- E. = film of dried serous exudates
- F. = small petechial erosions and/or scabs
- G. = no other effects

The Subject Local Tolerability Assessments will be performed according to the Schedule of Visits and Assessments ([Section 1.3](#)).

The Subject Local Tolerability Assessment will be administered by the site **10 to 15 minutes after investigational product application** in the clinic.

The subject will assess burning/stinging (0-3 score):

### **Local Tolerability Assessment**

Grade	Sensation Following Investigational Product Application
0 (none)	No sensation
1 (mild)	Slight warm, tingling sensation; not really bothersome
2 (moderate)	Definite warm, tingling sensation that is somewhat bothersome
3 (severe)	Hot, tingling/stinging sensation that has caused definite discomfort

### **5.1.9. Adverse Events**

Serious adverse events (SAEs) will be collected from the time the Informed Consent Form (ICF) is signed through 30 days after the last day of the application of the investigational product or the end of study (whichever is later).

Adverse events (AEs) will be collected following the first application of investigational product through the end of the study.

Please see [Section 5.7](#) for further details regarding the collection and reporting of adverse events.

## **5.2. Efficacy Evaluations**

### **5.2.1. Independent Rater Requirement**

To reduce possible functional unblinding and bias, independent raters will conduct efficacy assessments while separate trained members of the research team will conduct safety assessments and other activities of study oversight.

An independent rater is a trained research team member that is not aware of a subject's response to treatment as it pertains to safety including AEs such as local treatment site reactions.

The independent rater assigned for a subject:

- may conduct screening activities.
- have not participated in any activities prohibited for that role (e.g., safety assessments) following initial IP/phototherapy treatment for that subject.
- is not absolutely required to be the same person for each assessment, although it is strongly preferred that the same rater be used consistently wherever possible.

At the end of the study, the independent rater will be asked to complete an attestation to determine if they remain blinded as to the subject's treatment group.

### **5.2.2. Body Surface Area**

BSA assessments will be performed according to the Schedule of Visits and Assessments ([Section 1.3](#)).

The BSA affected with vitiligo will be assessed as a percentage of the total BSA, and will be determined to the nearest 0.01% using, as guides, the palm plus 5 digits, with fingers tucked together and thumb tucked to the side (handprint), as 1% BSA and the thumb as 0.1% BSA.

- Facial BSA (F-BSA) will be evaluated for the purpose of inclusion in the study. The area "Face" is defined as including the area on the forehead to the original hairline, on the cheek to the jawline vertically to the jawline and laterally from the corner of the mouth to the tragus. The area "Face" will not include surface area of the lips, scalp, ears, or neck but will include the eyelids and nose.
- F/N-BSA includes the BSA of the face and neck.
- BSA of the hands, forearms and elbows will include BSA affected with vitiligo in those aforementioned areas.
- BSA (total body) will include all areas of the body affected with vitiligo.

### **5.2.3. Vitiligo Area Scoring Index (VASI)**

Areas affected by depigmentation due to vitiligo will be assessed using the VASI, which is a quantitative clinical tool that is based on a composite estimate of the overall area of vitiligo patches at baseline and the degree of macular repigmentation within these patches over time. The reliability and validity of F-VASI and T-VASI instruments as measures of treatment efficacy were confirmed ([Rosmarin 2020](#)).

VASI is measured by percentage of vitiligo involvement (% of BSA) and the degree of depigmentation. The percentage of BSA (hand unit) vitiligo involvement is estimated by the Investigator using the Palmar Method. Hand unit is based on subject's hand size. The Investigator uses his/her hand to mimic the subject's hand size to evaluate percentage of BSA vitiligo involvement.

The following VASI scoring will be completed per the Schedule of Visits and Assessments ([Section 1.3](#)).

- F-VASI: The area "Face" is defined as the area included in the validation of F-VASI ([Rosmarin 2020](#)), with the additional inclusion of the eyelids. "Face" is defined as the area on the forehead to the original hairline, on the cheek to the jawline vertically to the jawline and laterally from the corner of the mouth to the tragus. The area "Face" will not include surface area of the lips, scalp, ears, or neck but will include the eyelids and nose.
- F/N-VASI: Includes the VASI of the face and neck
- FOREARM-VASI: Includes VASI (total score) of the Forearms and Elbows
- HAND-VASI: Includes VASI of the hands only

- T-VASI: Includes VASI of the following 6 **separate and mutually exclusive sites**: (1) head/neck, (2) hands, (3) upper extremities (excluding hands), (4) trunk, (5) lower extremities (excluding feet), and (6) feet.

The degree of depigmentation for each vitiligo involvement site is determined and estimated to the nearest of the following percentages: 0, 10%, 25%, 50%, 75%, 90%, or 100%. At 100% depigmentation, no pigment is present; at 90%, specks of pigment are present; at 75%, the depigmented area exceeds the pigmented area; at 50%, the depigmented and pigmented area are equal; at 25%, the pigmented area exceeds the depigmented area; at 10%, only specks of depigmentation are present.

The VASI is then derived by multiplying the values assessed for the vitiligo involvement by the percentage of affected skin for each site and summing the values of all sites together.

The percentage of vitiligo involvement is estimated in hand units by the same investigator during the entire course of the study.

